## Duloxetine hydrochloride (LY248686)

Phase IIIb, multicenter, randomized, double-blind, placebo-controlled, 13-week clinical trial to assess the efficacy and safety of duloxetine 30/60 mg QD compared to placebo in adolescents with Juvenile Primary Fibromyalgia Syndrome. Continued efficacy and safety of duloxetine 30/60 mg QD will be assessed in a 26-week, open-label treatment extension period.

Eli Lilly and Company  
Protocol F1J-MC-HMGW  
Phase IIIb

Statistical Analysis Plan Version 3 electronically signed and approved by Lilly on date provided below.

Statistical Analysis Plan Version 2 electronically signed and approved by Lilly on date 11Dec2014

Statistical Analysis Plan Version 1 electronically signed and approved by Lilly: 10Feb2011

Approval Date: 27-Jun-2017 GMT

### 3. Revision History

SAP version 1 was approved on 10Feb2011, and SAP version 2 was approved on 11Dec2014 both before unblinding. The following changes were made to the SAP since the version 1:

- In Section 5.3, added patients could be re-screened based on revised protocol (b).
- The section of 'Determination of Sample Size' was moved to Section 5.2 and updated to reflect more accurate assumptions around dropout rate.
- More details of patient population, baseline and post-baseline definitions for all efficacy and safety analyses are summarized in Table HMGW.6.1.
- The details of definition of treatment group for Study Period II/III were added in Section 6.1.2, and analyses for Study Period II/III were added in Section 6.1.13 and 6.1.14.
- Removed the potential DLX\_NOIP treatment group for SP IV in Section 6.1.2.
- In Section 6.1.4, a selection model and a placebo multiple imputation (pMI) approach were added to handle dropouts or missing data.
- The details of definition of baseline concurrent/ongoing therapies were added in Section 6.1.8.
- The details of definition of significant protocol deviations were added in Section 6.1.9 and summarized in Table HMGW.6.2.
- More details of definition of last dose date for Study Period II and Study Period III were added in Section 6.1.10.
- More details of the test of maintenance of effect were added in Section 6.1.13.2 and Section 4.2.
- Added Section 6.1.13.3 for sensitivity analysis and updated the sensitivity analysis employed.
- More details of definition of treatment-emergent adverse events (TEAE) for Study Period II and Study Period III were added in Section 6.1.14.1.
- The details of definition of normal values at baseline were added for treatment emergent and potentially clinically significant analyses in vital signs and ECGs in Section 6.1.14.3 and 6.1.14.4 respectively.
- Analyses for non-suicidal self-injurious behavior were added in Section 6.1.14.5.
- Adjusted paragraph order in the safety Section 6.1.14.
- The details of American College of Rheumatology (ACR) criteria for fibromyalgia (Wolfe et al. 1990) were added in Section 6.3.2.

- The section of 'Changes in the Conduct of the Study or Planned Analyses' was removed since it will be summarized in the clinical study report for this study.
- Update the Interim Analysis in Section 6.2.
- Removed Appendix 1 Details of Sensitivity Analysis and Appendix 2 Implementation of Placebo Multiple Imputation.

## 4. Study Objectives

### 4.1. Primary Objective

The primary objective of this study is to evaluate the efficacy of duloxetine 30/60 mg once daily (QD) compared with placebo on the reduction of average pain severity as measured by the Brief Pain Inventory (BPI) – Modified Short Form: Adolescent Version 24-hour average pain severity rating (for simplicity, it is referred to as the BPI average pain severity hereafter) during a 13-week, double-blind treatment phase in adolescents (aged 13 to 17 years) with Juvenile Primary Fibromyalgia Syndrome (JPFS), as defined by Yunus and Masi (Yunus and Masi 1985).

### 4.2. Secondary Objectives

The secondary objectives of the study are as follows:

- To evaluate the efficacy of duloxetine 30/60 mg QD in the treatment of adolescents with JPFS during a 13-week, double-blind treatment phase, based on the improvement of the following measures:
  - Brief Pain Inventory (BPI) Modified Short Form: Adolescent Version severity (worst pain, least pain, pain right now) and interference.
  - Response to treatment, as defined by a 30% and 50% reduction in the BPI average pain severity.
  - Pediatric Pain Questionnaire (PPQ) pain right now, worst pain and average pain items.
  - Clinical Global Impression of Severity for Overall Illness (CGI-Severity: Overall Illness) scale.
  - Clinical Global Impression of Severity for Mental Illness (CGI-Severity: Mental Illness) scale.
  - Functional Disability Inventory - child version scale (FDI-child).
  - Functional Disability Inventory - parent version scale (FDI-parent).
  - Children's Depression Inventory (CDI).
  - Multidimensional Anxiety Scale for Children (MASC).
- To evaluate the safety and tolerability of duloxetine 30/60 mg QD in the treatment of adolescents with JPFS during a 13-week, double-blind treatment phase.
- To evaluate the efficacy and safety of duloxetine 30/60 mg QD during a 26-week, open-label, extension treatment phase, as assessed by the following:
  - Maintenance effect of duloxetine 30/60 mg QD during the open-label extension treatment phase. Maintenance effect will be assessed using the BPI average pain severity in only the duloxetine treated acute phase responders (defined as those patients with  $\geq 30\%$  pain reduction from baseline on the BPI average pain severity measure at the last non-missing assessment in Study Period II).
  - Effect of duloxetine 30/60 mg QD during an extension treatment phase as measured by the following: BPI, PPQ, CGI-Severity: Overall Illness, CGI-Severity: Mental Illness, FDI-child, FDI-parent, CDI, and MASC.

- Safety of duloxetine 30/60 mg QD during an extension treatment phase.

### **4.3. Exploratory Objectives**

Exploratory objectives of the study are as follows:

- To evaluate the correlation between BPI pain severity items and PPQ pain items.
- To evaluate the appropriateness of the ACR FM criteria (Wolfe et al. 1990) in an adolescent population.

[figure not shown]
## 5. Study Elements

This section contains the summary of study design and the method of treatment assignment from Study F1J-MC-HMGW protocol.

### 5.1. Summary of Study Design

Study F1J-MC-HMGW (HMGW) is a Phase 3b, multicenter, randomized clinical trial of duloxetine versus placebo for the treatment of JPFS in adolescents. The study design includes 4 study periods. Following Study Period I (screening phase), eligible patients enter Study Period II, the acute 13-week parallel, randomized, double-blind, placebo-controlled treatment period of duloxetine 30/60 mg QD. Upon completion of the 13-week double-blind period, patients enter Study Period III, a 26-week, open-label extension phase of duloxetine 30/60 mg QD. A 1-week drug taper period (Study Period IV) is required for all patients who discontinue for any reason between Visit 4 to Visit 8 during Study Period II, or who complete/discontinue Study Period III on duloxetine 60 mg QD.

Figure HMGW.5.1 illustrates the study design.

Abbreviations: DB = double-blind; DLX = duloxetine; OL = open-label; QD = once-daily

a After Visit 3, patients increased to 60 mg duloxetine can have their dose decreased 1 time, at a scheduled or unscheduled Visit. Once 60 mg dose is decreased to 30 mg, it cannot be increased again during Study Period II.

b At Visits 4 through 8, patients randomized to placebo or DLX 30 mg who discontinue prior to entering the open-label extension treatment period (Study Period III) will receive placebo in the drug taper period.

c At Visits 9 through 14 in Study Period III, dose increases are permitted at scheduled visits (to a maximum dose of 60 mg QD) and dose decreases are permitted at scheduled or unscheduled visits (to a minimum dose of 30 mg QD).

d Patients who complete/discontinue Study Period III on DLX 30 mg do not need to enter the drug taper period.

**Figure HMGW.5.1** Illustration of study design for Protocol F1J-MC-HMGW.

Study Period I is a screening period of approximately 1 week in duration, but not more than 30 days, during which patients will be screened for study eligibility.

Study Period II is a 13-week, acute treatment period. During Study Period II, at Visit 2, patients who meet all study criteria for enrollment will be randomly assigned in a 1:1 ratio to duloxetine or placebo by a computer-generated random sequence using an interactive voice response system (IVRS). All patients will receive investigational product (IP) beginning at Visit 2 and will be instructed to start taking their IP the morning after Visit 2.

Patients randomly assigned to placebo will remain on placebo throughout Study Period II.

Patients randomly assigned to the duloxetine treatment group will remain on duloxetine throughout Study Period II. Duloxetine patients will initially take a 30 mg QD dose of duloxetine for 1 week. Starting at Visit 3 through Visit 6, the dose can be increased from 30 mg QD to 60 mg QD. By Visit 4, comorbid MDD and/or GAD patients receiving a 30-mg QD dose should be increased to a 60-mg QD dose, unless the patient is experiencing significant intolerance to the 30-mg dose. Beginning at Visit 7, no dose increases can be made. Dose-escalation criteria for all patients is based on investigator's clinical judgment. Dose increase can only occur at scheduled study visits. If necessary due to intolerability, for those patients on a 60-mg QD dose, a one-time dose decrease to 30 mg may occur at a scheduled or unscheduled visit. Once the 60-mg dose is decreased to 30 mg, it cannot be increased again during Study Period II. If the patient has already had their 1 dose decrease, and at a subsequent time cannot tolerate the investigational product dose well enough to remain compliant, the patient should be discontinued.

Study Period III is a 26-week, open-label extension treatment phase. Patients randomized either to the duloxetine or placebo treatment group during Study Period II will enter Study Period III on a 30-mg dose of duloxetine for 1 week. The duloxetine dose may be increased to 60 mg QD only at a scheduled Visit starting at Visit 9 (Week 14). As in Study Period II, additional dose-escalation consideration should be given to all patients with comorbid MDD and/or GAD at study entry. At Visit 9, the comorbid MDD and/or GAD patients should have their 30-mg dose increased to 60 mg, unless the patient is experiencing significant intolerance to the 30-mg dose. From Visit 9 to Visit 14, dose modifications are allowed. Dose increases (up to 60 mg QD) are only permitted at scheduled visits. Dose decreases (down to 30 mg QD) are permitted at either scheduled or unscheduled visits. Dose adjustments are to be based on the investigator's clinical judgment of treatment response and tolerability at the patient's current dose.

Study Period IV is a 1-week taper phase to minimize the occurrence of discontinuation-emergent adverse events (AEs). Patients who complete Study Period III or discontinue after Visit 9 of Study Period III while on duloxetine 60 mg QD, will receive duloxetine 30 mg QD for 1 week. The 1-week taper is not required for patients in Study Period III who complete or discontinue early on a 30-mg QD dose of duloxetine.

Patients who discontinue between Visits 4 to 8 of Study Period II should enter into the 1-week drug taper period. However, tapering of IP should be based on the investigator's determination of safety for his or her patient. Patients on duloxetine 60 mg QD will receive 30 mg QD for

1 week. Patients on duloxetine 30 mg QD will receive placebo for 1 week. Patients on placebo will receive placebo for 1 week. The 1-week taper is implemented in a blinded manner using the IVRS. The taper period is not required for patients who discontinue at Visit 3 and therefore have not received 2 weeks of treatment.

## **5.2. Determination of Sample Size**

Approximately 184 patients will be randomized in a 1:1 ratio to the duloxetine and placebo treatment groups. This study is to assess the difference of the mean change in BPI average pain severity from baseline to the last time point (Visit 8, Week 13) in Study Period II between treatment groups. Assuming that there will be some missing post-baseline data, and about 81% completion rate at acute phase by Visit 8 or Week 13, this sample size will provide at least 80% power to detect the treatment difference of 1.0 point with  $\alpha=.05$ . All the parameters used in the sample size calculations were based on the MMRM analysis of data from 3-month, placebo-controlled, acute treatment period in 2 adult FM studies: Study F1J-MC-HMCA and Study F1J-MC-HMCJ.

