#### 6.1.2. General Considerations

Efficacy and safety analyses will be done on an intent-to-treat (ITT) basis unless otherwise specified. An intent-to-treat analysis is an analysis of data by the groups to which patients are assigned by random allocation, even if the patient does not take the assigned treatment, does not receive the correct treatment, or otherwise does not follow the protocol.

All efficacy and safety analyses of continuous measures will include randomized patients with both a baseline and at least one post-baseline value for the variable being analyzed. For efficacy and continuous safety variables, baseline is defined as the last measurement taken at, or prior to the visit where the study period begins; endpoint is defined as the last non-missing measurement for the study period of interest. Table HMGW 6.1 provides baseline and post-baseline definitions for all variables.

Statistical analyses will be carried out for Study Period II, III, and IV (SP II-IV). All tests of hypotheses will be evaluated based on a two-sided significance level of 0.05 unless otherwise specified. No adjustments for multiple comparisons will be made.

For SP II, a patient's treatment group will be determined by the treatment to which the patient is randomized: either duloxetine (DLX) or placebo (PLA).

For SP III, the following treatment groups will be determined by the randomized treatment at SP II and extension phase treatment at SP III:

PLA/DLX: patients who are randomized to placebo at SP II and who enter SP III and take duloxetine.

DLX/DLX: patients who are randomized to duloxetine at SP II and who enter SP III and take duloxetine.

No statistical comparisons will be conducted to compare the two treatment groups PLA/DLX and DLX/DLX during SP III unless otherwise noted. For continuous measures, when appropriate, within treatment testing of change from baseline for selected safety and efficacy measures will be conducted for SP III.

For SP II/III, one treatment group will be determined by the randomized treatment at SP II:

DLX: patients who are randomized to duloxetine at SPII, including patients who may have discontinued early at SPII or who enter SPIII.

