## 6.2. Interim Analysis

Due to low patients enrollment throughout this study, Lilly provided FDA with a document (Sequence No. 0036) to request release from the post marketing requirement (PMR) in April 2014. FDA requested Lilly to explore the possibility of conducting an interim analysis of the efficacy data in their July 2014 written response. Lilly proposed a futility analysis which was

subsequently requested to conduct from FDA. The appropriate Lilly regulatory scientists were consulted and determined that the unplanned interim analysis plan will be documented in the SAP, and the protocol was not amended.

The interim analysis would focus on the primary efficacy analysis of duloxetine 30/60 mg once daily (QD) compared with placebo on the reduction of average pain severity as measured by the BPI average pain severity rating during the Study Period II in adolescents (aged 13 to 17 years) with JPFS. The purpose of the interim analysis is to evaluate the primary efficacy endpoint to stop the study early for futility using pre-specified decision rules, and it will not require adjustment of  $\alpha$ . Sites will remain blinded to any information produced from the interim analysis. A statistical analysis center (SAC), which would be external to the study team in order to maintain data integrity, will be unblinded and conducting the analyses in the restricted access folder, [https://sddchippewa.sas.com/webdav/lillyce/prd/ly248686/f1j\\_mc\\_hmgw/ac\\_unblinded1](https://sddchippewa.sas.com/webdav/lillyce/prd/ly248686/f1j_mc_hmgw/ac_unblinded1). The study team will remain blinded to the interim analysis data if the study continues. The SAC members will not be in contact with study site personnel.

The randomization cut-off date for the interim analysis will be the date when approximately 150 patients are randomized, which is approximately 71% of planned enrollment. The data lock for the interim analysis would occur approximately 3 months later to ensure those randomized patients will subsequently either complete or discontinue the double-blind treatment phase. The patient population for the interim analysis will be all patients randomized on or before the randomization cut-off date.

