The futility interim analysis will be based on the calculation of conditional power (CP). Conditional power represents the probability that the ongoing trial will result in statistically significant difference between duloxetine 30/60 mg QD and placebo at end of the trial, based on the data available at the time of interim analysis. The calculation of conditional power follows that proposed in Lan and Wittes (1988) and DeMets (2006). If  $Z(t)$  represents the test statistic at interim, then the conditional power for expected test statistic  $\theta$  (the assumed treatment effect) at end of trial could be calculated as following:

$$CP = 1 - \Phi \left\{ \frac{Z_{\alpha/2} - Z(t)\sqrt{t} - \theta(1-t)}{\sqrt{1-t}} \right\}$$

Where  $\Phi$  is the cumulative distribution function of the standard normal distribution,  $\alpha$  is the type I error for two-sided test, and  $t$  is the information fraction which defined as proportion of planned patients randomized at interim analysis. If assuming data at end of the trial will follow the trend observed at interim analysis, the calculation of conditional power could be simplified as following:

$$CP = 1 - \Phi \left\{ \frac{Z_{\alpha/2} - Z(t)/\sqrt{t}}{\sqrt{1-t}} \right\}$$

The test statistic  $Z(t)$  will be calculated based on estimators from primary efficacy analysis. The primary efficacy analysis will be the contrast between duloxetine 30/60 mg QD and placebo at the last visit during double-blind treatment phase (Visit 8, Week 13) from a mixed model repeated measures analysis (MMRM) on change from baseline in BPI average pain severity. The model will include the fixed categorical effect of treatment, pooled investigate site, visit, and treatment-by-visit interaction, as well as the continuous, fixed covariate of baseline value of BPI average pain severity and baseline value of BPI average pain severity-by-visit interaction. The test statistic at interim will be approximately calculated as  $Z(\hat{t}) = \hat{\delta}/se(\hat{\delta})$ , where  $\hat{\delta}$  is the estimator of the contrast between duloxetine 30/60 mg QD and placebo at Week 13, and  $se(\hat{\delta})$  is the corresponding standard error.

The SAC will only communicate one of the two possible decisions to Lilly:

- Conditional Power (CP)  $<0.6$ : Trial termination for futility
- Conditional Power (CP)  $\geq 0.6$ : Trial may continue

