with the pre-determined Lilly individuals (medical director, regulatory scientist, statistician, clinical trial manager, chief operating officer, and clinical project management advisor) in order to decide further study implementation. The outline of the plan will be based on the document that Lilly submitted to FDA on September 2, 2014, containing Lilly responses to the FDA guidance provided in the written responses dated July 11, 2014 titled "Response to FDA's Information Request Regarding Release from Post Marketing Requirement for Adolescents with Fibromyalgia: Study F1J-MC-HMGW" (Sequence No. 0037).

The SAC will inform the FDA project manager of the primary efficacy results from a mixed model repeated measures analysis (MMRM) on change from baseline in BPI average pain severity as well as the conditional power. This will be sent by a password protected encrypted file with a cover letter.

When the CP meets the criterion of futility stopping rule, and the study is terminated early, the sensitivity analyses to address the impact of missing data on primary efficacy analysis may not be performed.

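### The 80% power in Section 5.2 leaves out the Section 6.2 futility stop; if power at full size is exactly 80%, the rule as written leaves about 72–75%

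*SAP*

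**What the plan says.** Section 5.2 of the SAP fixes the size: "Approximately 184 patients will be randomized in a 1:1 ratio to the duloxetine and placebo treatment groups". It states that "this sample size will provide at least 80% power to detect the treatment difference of 1.0 point", assuming about 81% completion at Week 13 and parameters taken from two adult studies. It mentions no interim analysis.

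Section 6.2 adds an unplanned futility look. The cut-off date "will be the date when approximately 150 patients are randomized, which is approximately 71% of planned enrollment". The decision rests on conditional power (CP), in which t "is the information fraction which defined as proportion of planned patients randomized at interim analysis". Two formulas are given. The first uses an assumed effect θ, to which no number is attached. The second covers the case where the observed trend continues, for which "the calculation of conditional power could be simplified as following". Neither is named as the one compared with 0.6. The result for CP below 0.6 reads "Trial termination for futility". It goes to a set of sponsor roles "in order to decide further study implementation".

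On error rates, Section 6.2 says only that alpha needs no adjustment. It does not mention power. The revision history in Section 3 records an update of the sample-size section for dropout and an update of the interim section, with no link between them.

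**The concern.** A futility stop can only lower power, because some trials that would have reached significance at full size are ended early. The loss is small when the CP cut is low. Here the cut is 0.6 with more than 80% of the patients already in, so a trial must be close to significance at the look in order to continue. Under the trend formula the cut is an interim Z of 1.87, a two-sided p of about 0.06.

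The reader of Section 5.2 is told the risk of missing a 1.0-point effect is at most 20%. If the rule is followed, that may not be so. It matters for interpretation: a futility stop would bear on a post-marketing requirement, and whoever reads it needs to know how often this rule stops a trial in which the drug works as assumed.

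The open choice of formula and the unmatched 71% belong to the same point. Both enter the decision directly and both change the size of the loss.

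**Working it through.** **Inputs from the SAP**
- Two-sided α = 0.05 (Section 6.1.2: "All tests of hypotheses will be evaluated based on a two-sided significance level of 0.05 unless otherwise specified"), so z = 1.960.
- Planned N = 184, power at least 80% for 1.0 point, 81% completion (Section 5.2).
- Look at about 150 randomized, stop if CP < 0.6 (Section 6.2). The 0.6 quantile of the normal is 0.2533.
- t = 150/184 = 0.815, from the SAP's own definition of t and its only stated planned size. √t = 0.903, √(1−t) = 0.430.

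**The plan's own 80%.** It cannot be recomputed directly, because no SD or covariance is given. Working back from exactly 80%, SD = 1/(√(2/n) × 2.802). This gives 2.18 on completers only (n = 92 × 0.81 = 74.5 per arm) and 2.42 if all 92 per arm contribute. The figure is plausible for a trial run to full size.

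**Drift.** At 80% full-size power the expected final statistic is θ = 1.960 + 0.842 = 2.802. The expected interim statistic is θ√t = 2.530. Positive Z favours duloxetine.

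**Interim cut, solving CP ≥ 0.6 for Z(t)**
- Current trend: Z ≥ √t × (1.960 + 0.2533√(1−t)) = 0.903 × 2.069 = 1.868.
- Assumed effect, with θ set to 2.802: Z ≥ (1.960 + 0.2533√(1−t) − θ(1−t))/√t = (2.069 − 0.518)/0.903 = 1.718.

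**Chance of stopping under a true 1.0-point effect**, Φ(cut − θ√t)
- Current trend: Φ(1.868 − 2.530) = 25.4%.
- Assumed effect: Φ(1.718 − 2.530) = 20.9%.

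**Overall power** is P(Z(t) ≥ cut and Z(1) ≥ 1.96), bivariate normal with correlation √t. It is 71.6% (trend) and 74.6% (assumed effect). Simulation gives the same values.

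**Dependence on full-size power**, t = 0.815, rule followed

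| Full-size power | Stop: trend / assumed | Overall power: trend / assumed |
|---|---|---|
| 80% | 25.4% / 20.9% | 71.6% / 74.6% |
| 85% | 20.1% / 15.2% | 77.5% / 80.8% |
| 90% | 14.5% / 9.7% | 83.8% / 87.1% |

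For exactly 80% after the rule, full-size power must be 87.1% (trend) or 84.4% (assumed effect).

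**Dependence on the 71%**, starting from 80% power at N = 184

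| Reading of the 71% | Overall power: trend / assumed |
|---|---|
| 0.71 entered in the formula, true fraction 0.815 | 73.7% / 77.2% |
| About 211 planned (150/0.71), full-size power then 85.1% | 74.8% / 80.4% |
| True fraction 0.71 with full-size power still 80% | 68.6% / 73.6% |

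**The case against.** The strongest reply is that Section 5.2 is not shown to be false. It gives the power of a sample size, and 184 patients analysed at full size may well have it. It says at least 80% and gives no SD, so the true figure could be higher; at 90% both formulas leave more than 80%. This stands as a condition. It does not remove the point, because 80% is all the SAP guarantees.

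Second, the stop may be advisory, since the result goes to sponsor roles who decide on implementation. If stops could be overridden, less power would be lost. Purely as an illustration, overriding half of them would leave about 76% (trend) or 77% (assumed effect). But the outcome is labelled termination, the rules are called pre-specified, and no grounds for override are given.

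Third, the 72–75% range fixes t at 0.815 and θ at 2.80, while the SAP leaves both open. That is fair. The readings above run from about 69% to 80%, and one of them (about 211 planned, assumed effect) just meets 80%. The value 0.815 is used because it follows from the SAP's own definition and its only stated N.

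Finally, the operating characteristics may be in the regulatory submission that Section 6.2 cites, which is not available here. Only their absence from the SAP can be claimed. That the look was unplanned explains why the power calculation did not include it at first, but the current SAP contains both sections.

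**Conclusion.** The point holds. The SAP states a power that the design with its futility stop is not shown to deliver. If full-size power is 80%, t = 150/184 and the stop is followed, the risk of missing a true 1.0-point effect rises from 20% to about 28% (trend) or 25% (assumed effect). The arithmetic is firm; its premise, full-size power of exactly 80%, is the minimum the SAP guarantees and could be exceeded.

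Two defects need no assumption about power. The formula compared with 0.6 is not named, and 150 is called 71% of an enrollment that Section 5.2 puts at 184. Until both are settled, the external analysis center cannot apply the rule without guessing.

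**What to change.** In Section 5.2, say that the 80% applies to a trial run to full size. Add the power with the Section 6.2 rule included and the probability of a futility stop under the 1.0-point effect. If full-size power is 80%, these are about 72% and 25% (trend) or 75% and 21% (assumed effect). Otherwise, derive them from the sponsor's actual full-size power.

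In Section 6.2, name the one CP formula compared with 0.6; if it is the assumed-effect form, give θ a number. Reconcile the 71% with the planned size: if 184 stands, the figure is 82% and t is 0.82. If a different planned number lies behind the 71%, change Section 5.2 to match and recompute. State also whether the stop is binding.

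The 0.6 cut need not change. The cost is SAP wording and a short calculation. The stated power will look less favourable unless full-size power is at least about 84% (assumed effect) or 87% (trend).
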